1.3 Reactive case detection (RACD)

For elimination, active surveillance in the communities around passively detected index cases, reactive surveillance or reactive case detection, is recommended as a strategy to identify secondary cases and hot

spots.[2-4] However, re-active surveillance can be low yield, labor-intensive, and costly.[4] Microscopy is being replaced by antigen-based rapid diagnostic tests (RDTs) that provide convenience but have limitations in the sensitivity to detect low parasite density and non-falciparum infections.[5, 6] PCR offers markedly improved sensitivity, but it requires hours of processing time, sophisticated technical skill, and expensive equipment to perform. Loop mediated isothermal amplification (LAMP) offers the sensitivity of PCR and is easier to perform but the requirement that samples be performed in a laboratory limit its usefulness for population level screening and treatment.

Household members and neighbors around index cases harbor infection

In Swaziland, reactive case detection involves the screening of household members and neighbors residing within 500 meters of the index case. Preliminary data from reactive case detection in Swaziland show that reactive case detection is a useful strategy to find asymptomatic infections and hot spots. From September 2012 to April 2014, 74 additional infections were identified by LAMP in households and neighbors of 263 index cases, resulting in a 28% increase in the detection of infections. Residence near the index case was associated with a higher risk of infection. Residing within 100 meters of index case was associated with a 4.6 higher odds (95% CI 2.0 to 10.6) of infection compared to a baseline OR of 1.0 at 201-500m. Travel outside Swaziland and Mozambican nationality were associated with infection. However, excluding these individuals resulted in a similar finding: residing within 100 meters of index case was associated with a 4.2 higher odds (95% CI 1.7 to 10.4) of infection compared to a baseline OR of 1.0 at 201-500m (Figure 3).

[figure not shown]

Figure 3. LAMP positivity by distance from index case

Challenges with reactive case detection

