In this study, we will utilize a cluster randomized controlled study design to evaluate TPE and compare it to RACD in response to a passive identified index case. As both locally acquired and imported infections contribute to Swaziland's overall malaria burden and can cause onward transmission, individuals who

acquired their *Plasmodium* infections within their community and abroad will both be included as index cases triggering a response.

Effectiveness to interrupt transmission is an obvious outcome of interest for this study. Entomologic inoculation rate (EIR) is the gold standard measure of transmission; however, given the extremely low sporozoite rates among mosquitoes in low transmission settings such as Swaziland, this is an impractical measure for this study. Instead, for *our primary outcome*, we will measure the locality or cluster-level cumulative incidence of malaria cases over two transmission seasons. As secondary outcomes measures of effectiveness, we will also measure proportion of imported incident cases, as well as the time to first subsequent incident local case post-intervention. While incidence is a standard measure captured through health facility reports, it does not capture asymptomatic infections in the community. Therefore, we will also conduct a cross sectional survey toward the end of the study (estimated mid 2017) at the end of the transmission season to measure seroprevalence and prevalence. Finally, we will measure transmission potential as measured by relatedness of detected infections (from passive surveillance or the follow-up survey) using genotyping. These additional measures of transmission were not selected as primary outcome measures for several reasons. Seroprevalence and genotyping are exciting but still investigational diagnostic methods. Post-intervention prevalence of asexual and sexual stages may be too low for comparison though we will optimize our chances of detecting infection by collected higher volumes of blood and focusing in the highest risk areas (Target Areas). Nonetheless, we will evaluate these measures of effectiveness and may be able to find that one arm is superior to another for a particular outcome measure. These findings will be useful for Swaziland and for higher endemic settings where it might be easier to evaluate impact.

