Finally, cluster randomized controlled trials are the gold standard to compare health services and policy interventions, but significant inputs in time and resources are usually required rendering this study design impractical in program settings. However, as we propose in this project, when many cases are easily available (index cases reported through passive surveillance), existing infrastructure is in place (the current

surveillance team), and the outcome measures can be feasibly measured (incidence will be collected through routine case reporting data, with secondary outcomes measures mainly collected through minimal follow-up visits), a cluster randomized controlled trial can be performed quickly and efficiently.

3 Study aims

The **overall objective** of this proposal is to critically evaluate TPE vs. RACD as a surveillance and response strategy for malaria elimination.

Our **primary aim** is to:

Compare the impact of TPE versus RACD on incidence of malaria cases. We will test the hypothesis that TPE compared to RACD will result in a lower cumulative incidence.

In addition, the following **secondary aims** will be addressed:

Effectiveness:

1. To compare the impact of TPE versus RACD on seroprevalence. We will test the hypothesis that TPE, compared to RACD, will result in lower exposure to malaria, as assessed by antibodies to antigenic markers of recent exposure near the end of the study period (expected mid 2017).
2. To compare the impact of TPE versus RACD on prevalence of infection. We will test the hypothesis that TPE, compared to RACD, will be more effective in decreasing the prevalence of infection near the end of the study period (expected mid 2017).
3. To compare the impact of TPE versus RACD on the proportion of imported incident cases. We will test the hypothesis that TPE compared to RACD will result in a higher proportion of imported incident cases.
4. To compare the impact of TPE versus RACD on time to first incident local case subsequent to the intervention. We will test the hypothesis that TPE compared to RACD will result in a longer time to the first incident local case.
5. To compare the impact of TPE versus RACD on transmission potential, measured by relatedness of strains by microsatellite genotyping. We will test the hypothesis strains detected in TPE versus RACD are less related to ancestor infections.

Feasibility:

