4.1 Overview

We will evaluate the impact and feasibility of TPE versus RACD as a surveillance and response strategy in the communities around passively detected index cases using a cluster-randomized trial umbrella study design. To facilitate operations of the trial and subsequent roll-out of the TPE intervention should it be shown to be effective and feasible, the randomization will occur at the administrative level of the locality. A total of 77 historically at-risk study localities or clusters will be included in the trial; 39 will be randomized to the TPE intervention, and 38 to the control intervention (RACD) (Figure 4). If new malaria hotspots are detected during the study period, these additional localities may also be included in the study at the discretion of the study team, in consultation with the Swaziland National Malaria Control Programme. These additional study localities will be randomly assigned to receive either the RACD or the TPE intervention. Target areas for localities randomized to receive TPE will be defined as all individuals residing within 200m of an index case that is detected in passive surveillance and resides in a TPE locality, with individuals residing immediately beyond 200m included if a minimum of 30 individuals are not enrolled within 200m. Target areas for localities randomized to receive RACD will be defined as all individuals residing within 500m of an index case that is detected in passive surveillance and resides in a RACD locality (as per current policy in Swaziland), while focusing on maximizing coverage within the immediate 200m radius around the index case. Per current policy, for individuals receiving RACD, blood will be collected for RDT and DBS and subjects testing positive on RDT will be referred to a local clinic for treatment with AL. In the TPE arm, blood will not be collected and presumptive treatment will be administered by modified DOT. Incidence data will be collected passively during the study period. For secondary outcome measures, in select Target Areas, a pill count will be conducted 7-10 days after the first visit day and a qualitative Acceptability Assessment will be conducted with study participants at the time of the pill count. Passive monitoring for serious adverse events (SAEs) will occur in both the TPE and the RACD arms. To measure prevalence and seroprevalence, a cross sectional survey will be conducted in Target Areas near the end of the study (during the end-line survey, expected to take place mid 2017). Finally, to validate the serological markers, a follow-up survey will be conducted at 6-9 months among any individuals who were infected at baseline (index cases in both arms as well as secondary cases detected by RDT at baseline in the RACD arm).

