14.2 Outcome measures

Table 6. Outcome measures

Outcome	Indicator
Primary Aim	
Incidence	Cumulative incidence of all cases (Pf infection) identified by passive surveillance in the locality subsequent to the first reported case during the study period (not including additional cases found through RACD). Cases include both locally acquired and imported infections.
Secondary aims (effectiveness)	
Exposure (seroprevalence)	Seroprevalence to markers of recent exposure using ELISA in end-line survey samples taken from residents in Target Areas near the end of the study (expected mid 2017), excluding index cases detected through passive surveillance.
Infection prevalence	Prevalence of infection by LAMP and QTNASBA testing for gametocytes in LAMP positives in end-line survey samples taken from residents in Target Areas near the end of the study (expected mid 2017), including index cases detected through passive surveillance.
Time to first local post-intervention incident case	Time to first incident local case in the Target Area subsequent to the intervention. Target Areas that receive a repeat intervention will qualify to be included again at subsequent interventions.
Proportion of imported incident cases	Proportion of imported incident cases in the locality subsequent to the first reported case will be measured through passive surveillance. Additional cases found through RACD will not be included.
Transmission potential (by genotyping)	Microsatellite genotyping will be performed on samples collected from index cases as well as secondary cases.
Secondary aims (feasibility)	
Coverage	Proportion of persons residing within approximately 200m (TPE localities) or 500m (RACD localities) of the index case who consented to participate in the study and who completed the initial procedures for their study arm (finger prick for RDT in the RACD arm, initial dose of DP in the TPE arm)
Adherence	Proportion of persons who completed 3 days of therapy among all individuals initiated on DP in the TPE arm, as assessed by pill count
Prevalence of SAEs related to treatment	Proportion of subjects experiencing SAEs deemed possibly, probably, or definitely related to DP or AL, out of the total number of subjects enrolled
Acceptability	Qualitative assessment (See Section 10)
Cost	Cost per index case-level intervention, cost per case averted.

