Based on equation 4 from Hayes and Bennett International Journal of Epidemiology 1999;28:319-32

Assumes that population is only those in the EAs that have at least one case.

Sample size calculation based on harmonic mean of population size.

Table 8. Detectable reductions in seroprevalence given varying assumptions about prevalence in the RACD arm

# Total localities with at least one index case	# localities per arm	Number assessed per locality (n)		Outcome proportion		Km (coeff of variation)	Z beta	Power
		RACD	TPE	RACD (π_0)	TPE (π_1)			
46.6	23.3	60	60	3.00%	1.35%	0.9	0.84	80%
62.3	31.2	60	60	2.40%	1.18%	0.9	0.84	80%
49.3	24.7	60	60	2.00%	0.83%	0.9	0.84	80%
50.8	25.4	60	60	1.50%	0.57%	0.9	0.84	80%

Based on equation 4 from Hayes and Bennett International Journal of Epidemiology 1999; 28:319-326

Assumes we are including only persons in the target areas in the denominator but evaluating at locality level

Assumes 3 per 100 is the background seroprevalence

Table 9. Sample sizes for primary and secondary aims.

Outcome	Result*	Actual sample size (Effective sample size, based on harmonic mean in clusters)
Primary aim		
Incidence	0.4% (RACD) vs. 0.2% (TPE)	55,928 (41,328)
Secondary aims (effectiveness)		
Exposure (seroprevalence)	2.4% (RACD) vs. 1.18% (TPE)	5400 not including index cases (3720)
Infection prevalence	n/a	5600 includes index cases
Time to first post-intervention incident case	n/a	55,928 (41,328)

Outcome	Result*	Actual sample size (Effective sample size, based on harmonic mean in clusters)
Proportion of imported incident cases	n/a	55,928 (41,328)
Transmission potential	n/a	Genotyping estimated to be performed in 800 index cases** and 35 infections from follow-up cross sectional survey
Secondary aims (feasibility)		
Coverage in TPE Arm	80% (95% CI: 77%-83%)	1782
Adherence in TPE Arm	80%	532
Prevalence of SAEs related to treatment	n/a	5400 not including index cases (3720)
Acceptability	n/a	5400 not including index cases (3720)
Cost	n/a	10 Target Areas/arm

*for some secondary outcomes, power calculations were not performed however effective sample size is shown.

** 200 index cases will be from the study area but an estimated 600 DBS that are already collected as standard surveillance from other parts of the country will also be used to characterize the background genotypes/transmission potential in Swaziland, as it relates to the transmission potential in the study areas.

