4. Comparison of time to first post-intervention incident infection. We hypothesize that time to the first post-intervention index case within the Target Area will be longer for Target Areas receiving TPE compared to those receiving RACD. Analysis for this outcome will use a standard cox proportional hazards model to estimate the time to a subsequent incident infection among individuals in the Target Area.
5. Comparison of transmission potential using genotyping. Microsatellite genotyping will be used to measure transmission potential. DNA samples for genotyping will be collected from index cases and secondary cases. Based on malaria rates in Swaziland over the past three years, we expect approximately 200 index cases over the study period and 35 infections from the follow-up cross sectional survey (1.6% prevalence in the TPE arm and 0.4% in the RACD arm). We expect transmission potential to be lower in the TPE versus RACD arm. Relatedness of infections within Target Areas and within localities will be used as a surrogate for transmission potential.

Planned Analyses of Operational Feasibility and expected findings:

1. Coverage of the intervention. The numbers and proportion of the population completing finger prick testing (if RACD arm) or receiving at least the first dose of medication (if TPE) will be calculated by arm. The proportion of the individuals living in Target Areas around an index case that receive the TPE intervention is expected to be 80% with a 95% confidence interval from 76% to 84%.
2. Adherence to TPE. In the subsample of Target Areas surrounding the first index case in each locality assigned to TPE, we will assess adherence to the 3 day regimen of DP in TPE using pill count. We expect adherence to be 80%.
3. Safety of the TPE treatment. The number and percent of individuals experiencing an adverse event will be recorded by study arm. We expect that compared to RACD, TPE will be safely administered with few or no serious adverse events related to treatment, and no difference in SAEs compared to AL based on analysis of the adverse events report forms.
4. Acceptability of the intervention. See Section 10.
5. Costs per incident infection and per population. Detailed costing will be performed in 10 Target Areas per arm. We expect that costs per incident infection and per population for implementing the TPE intervention will be no higher than for RACD, the current standard of care.

15 Advisory Committee

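### The genotyping outcome admits secondary cases that come mostly from RACD-visit testing, so sampling differs by arm and can bias the relatedness comparison

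*Combined protocol and SAP*

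**What the plan says.** Table 6 (section 14.2) defines the samples for transmission potential: "Microsatellite genotyping will be performed on samples collected from index cases as well as secondary cases". Section 14.4, secondary analysis 5, repeats this ("DNA samples for genotyping will be collected from index cases and secondary cases") and gives the metric: "Relatedness of infections within Target Areas and within localities will be used as a surrogate for transmission potential". The hypothesis in section 3 has a direction: "We will test the hypothesis strains detected in TPE versus RACD are less related to ancestor infections". No relatedness statistic, pair definition or time window is given.

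Blood collection at the intervention visit differs by arm. In RACD every consenting resident is tested and gives a DBS, and RDT-positives also give a microtainer sample, partly to help genotyping (7.2). The study summary lists genotyping for the blood survey at Target Area enrolment, and that survey is in RACD only. For TPE, section 4.1 says: "In the TPE arm, blood will not be collected and presumptive treatment will be administered by modified DOT". The exception is residents who cannot safely receive DP. They get an RDT and DBS, plus a microtainer if positive (7.3 and Table 4).

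Three places describe the outcome differently. Section 2 (rationale for the selected outcomes) speaks of "relatedness of detected infections (from passive surveillance or the follow-up survey) using genotyping". Table 9 reads "Genotyping estimated to be performed in 800 index cases and 35 infections from follow-up cross sectional survey", of which 200 index cases are from the study area. Section 14.4 item 5, straight after naming secondary cases, counts only about 200 index cases and 35 end-line infections.

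For two other outcomes, cumulative incidence and proportion imported, Table 6 explicitly leaves out cases found through RACD. The genotyping row has no such exclusion.

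**The concern.** A between-arm comparison is protected by randomization only if the observations entering it are collected alike in both arms. Read as written, Table 6 and 14.4 bring in infections found by testing the neighbours of an index case. One arm tests everybody at that visit and the other tests only a minority.

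These infections were also acquired before the visit at which they are found, so they cannot show the effect of that visit's intervention. The protocol applies the same logic to seroprevalence, where it drops the first index case of each Target Area because exposure came before the intervention (14.1, 14.3).

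At stake is a secondary effectiveness outcome with a stated directional hypothesis. A difference in relatedness could reflect who was sampled and not what TPE did. The primary outcome is not affected.

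**Working it through.** **1. The plan's own counts.** Section 4.4 expects about 134 index cases per year. Two years give 2 x 134 = 268, or 134 per arm. Halving the TPE arm gives 67, and 134 + 67 = 201, against the stated 200 (14.1). Section 14.3 puts 66 in TPE, so RACD has 200 - 66 = 134. The 1,782 treated in TPE also reproduces: 66 x 30 x 0.9 = 1,782.

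The 35 end-line infections in 14.4 do not reproduce from the printed prevalences (1.6% TPE, 0.4% RACD). An equal split of 5,400 gives 2,700 x 0.016 + 2,700 x 0.004 = 54.0. The closest reading tried, an equal split of the effective 3,720, gives 1,860 x 0.016 + 1,860 x 0.004 = 37.2. The printed prevalences also run against the section 3 hypothesis of lower prevalence in TPE. Both are side points and do not enter the steps below.

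**2. Secondary infections per index case.**
- RDT: 42 positives among 8,355 screened (1.3) is 0.503%. With 30 people per Target Area (14.1), 30 x 0.00503 = 0.151.
- LAMP: section 1.3 reports "74 additional infections were identified by LAMP in households and neighbors of 263 index cases", so 74/263 = 0.281.

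**3. Expected infections found at the intervention visit, assuming no effect.** Expected number = index cases x yield x share of residents tested. The share is 1 in RACD. In TPE it is f, the DP-ineligible share. The documents do not give f, so 5-30% is assumed.

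| | RDT yield | LAMP yield |
|---|---|---|
| RACD, 134 index cases | 134 x 0.151 = 20.2 | 134 x 0.281 = 37.7 |
| TPE, 134 index cases, f = 5% to 30% | 1.0 to 6.1 | 1.9 to 11.3 |
| TPE, planned 66 index cases, f = 5% to 30% | 0.5 to 3.0 | 0.9 to 5.6 |

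The RACD share of these infections is 1/(1 + f) with equal index cases: 95% at f = 5% and 77% at f = 30%. With 66 TPE index cases it is 87% to 98%.

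**4. Direction of the bias.** Assumed, with identical transmission in both arms: 134 Target Areas per arm, f = 10%, and p later passive cases per Target Area. Let s be the secondary cases sampled per Target Area (0.151 in RACD and 0.0151 in TPE at the RDT yield). Let r_s and r_p be the probabilities that a secondary or a later passive case is related to the index case.

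- Share of index-linked pairs that are related = (r_s s + r_p p)/(s + p).
- Share of Target Areas with at least one related infection = 1 - exp(-(r_s s + r_p p)), with Poisson counts.

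Example: r_s = 0.6, r_p = 0.3, p = 0.2 gives a RACD pair share of (0.6 x 0.151 + 0.3 x 0.2)/0.351 = 0.429. Simulated values at p = 0.2:

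| Yield | r_s, r_p | Related pairs, RACD vs TPE | Areas with any related infection, RACD vs TPE |
|---|---|---|---|
| RDT | 0.4, 0.4 | 0.399 vs 0.402 | 0.130 vs 0.083 |
| RDT | 0.6, 0.3 | 0.429 vs 0.320 | 0.139 vs 0.067 |
| RDT | 0.3, 0.6 | 0.471 vs 0.578 | 0.153 vs 0.117 |
| LAMP | 0.4, 0.4 | 0.399 vs 0.400 | 0.173 vs 0.087 |
| LAMP | 0.6, 0.3 | 0.475 vs 0.340 | 0.205 vs 0.074 |
| LAMP | 0.3, 0.6 | 0.425 vs 0.568 | 0.184 vs 0.121 |

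The any-related measure was higher in RACD in all 20 scenarios run (five r_s, r_p pairs, p = 0.2 or 0.5, both yields). The pair share was equal, higher or lower in RACD depending on whether r_s equals, exceeds or falls below r_p.

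**The case against.** A reader might infer that sampling alone must raise relatedness in RACD, so that TPE is favoured whatever the truth. The documents do not support that. They give no relatedness data and no statistic, and step 4 shows that a mean pairwise measure can be unbiased or biased against TPE. That index-secondary pairs are more related is plausible: they are found close in time and place, and section 1.3 reports 4.6 times the odds of infection within 100 m compared with 201-500 m. It remains an assumption.

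Three further points for the plan stand in part.
- TPE does not contribute nothing. Its DP-ineligible residents are tested, and they include people with recent fever. The case form (Appendix C, item 51) also has a category for secondary cases identified at a health facility, which can arise in either arm.
- The LAMP figure of 38 is an upper end. Section 7.2 says microsatellites amplify poorly from DBS in asymptomatic people, and only RDT-positives give a microtainer at the visit. About 20 is the more realistic number of usable genotypes.
- Section 2, Table 9 and the counts in 14.4 name only sources common to both arms, so the authors may have meant those. Yet the sentences that define the outcome and its samples say otherwise, and nothing in the text resolves the conflict.

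The outcome is secondary, has no power calculation, and uses a method that section 2 calls investigational. That limits the weight of the point but does not remove it.

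**Conclusion.** The point holds as a conflict in the text and as arm-dependent sampling. If Table 6 and 14.4 are followed, about 20 to 38 infections found at the visit enter from RACD, against about 1 to 11 from TPE under no effect. RACD supplies roughly 77% to 98% of them, depending on f and on whether TPE has 134 or 66 index cases. The figures rest on past RACD yields, 30 people per Target Area for the RDT figure, and an assumed 5-30% tested in TPE.

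The direction is settled only for a count or any-related-infection measure, which would favour TPE with no effect. For a mean pairwise measure it depends on pair relatedness that the documents do not report. A claim that the design always favours TPE goes too far.

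Two features would remain if secondary cases were simply dropped by label. RACD secondary cases are relabelled as index cases (4.4, 7.2), although Table 3 excludes infections found by screening from that role. And Target Areas extend 200 m in TPE (further if fewer than 30 are enrolled) but 500 m in RACD, so relatedness within a Target Area is measured over different areas. The wider RACD radius could dilute relatedness there.

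**What to change.** In Table 6 and 14.4 item 5:

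1. Restrict the between-arm relatedness comparison, by mode of detection, to passively detected cases and end-line survey infections.
2. Exclude infections found at the intervention visit in either arm, including RACD secondary cases that were relabelled as index cases. Item 51 of the case form already separates secondary cases from RACD from those identified at a health facility; keep the latter. That item has no option worded for an infection found at a TPE visit, so state how those few will be flagged.
3. Compare relatedness within one common radius around the index case in both arms.
4. Name the relatedness statistic and the pairs that enter it.
5. Use genotypes from the intervention visit for description and method development only.

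Align section 2, Table 9 and the study summary with this wording. The cost is a few sentences and no new samples. Fewer genotypes enter the comparison, mainly on the RACD side: about 20 to 38 on the yields above.
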